#### 5.7.5 **Dose Specifications:**

A dose of 50 Gy in 25 daily fractions for extremity STS and 45 to 50.4 Gy in 28 fractions for retroperitoneal STS will be prescribed to the planning target volume (PTV) using linear accelerator and megavoltage photon beams with energies of 6MV or greater.

For retroperitoneal/intra-abdominal sarcomas, a dose-painted simultaneous integrated boost (SIB) to total dose of 57.5 Gy in 25 fractions is allowed in select cases. A postoperative EBRT boost is discouraged.

Prescribed dose should cover > 90% of the PTV. More than 95% of the PTV should receive > 95% of the prescribed dose. No more than 20% of the PTV will receive  $\geq 110\%$  prescription dose.

#### 5.7.6 **Precautions and Dose Constraints for critical structures:**

Radiation dose to normal tissues should be kept within the accepted normal tissue tolerances. Every effort should be made to:

- a) Avoid treating the full circumference of an extremity;
- b) Avoid treating anus, urogenital tract, perineum and genitalia; if the tumor is close to these structures, typically less than 50% volume of the anus and vulva should receive 30 Gy; less than 50% volume of the testis should receive 3 Gy, if the patient prefers to reserve fertility;
- c) Avoid treating the lung, through use of appropriate shielding and treatment planning; less than 20% of the lungs should receive 20 Gy (V20);
- d) Avoid dose maximums in areas where surgical scars will be placed; this may require reviewing treatment plans with the surgeon;
- e) If possible, avoid treating skin over areas commonly traumatized to full dose (e.g., the elbow, knee, shin, femoral neck).
- f) If possible, less than 50% of any joints (including shoulder, elbow and knee) should receive 50 Gy.
- g) Less than 50% of kidney volumes should receive 18 Gy.
- h) No more than 50% of normal weight-bearing bone within the radiation field should receive 50 Gy except when the tumor invades the bone or when there is circumferential involvement of the tumor more than a quarter of the bone or when the bone will be resected in a subsequent surgical resection after radiation.

For any other normal tissue structures, no radiation dose more than the established TD5/5 limit should be given.

#### 5.7.7 **Image Guidance and Verification Devices**

Portal films or conebeam CT images should be used for target localization and alignment. Daily cone beam CT will be preferred and dose from daily cone beam should be included

in the final dosimetry.

### 5.7.8 **Simultaneous Integrated Boost**

A simultaneous integrated boost to a total dose of 57.5 Gy in 25 fractions is allowed for patients in whom the surgeon feels a margin negative resection will be difficult to achieve. The boost volume is defined as the high-risk retroperitoneal margin jointly identified by the surgeon and treating radiation oncologist. In this scenario, no further postoperative boost is allowed.

### 5.7.9 **Postoperative Radiotherapy Boost**

An External Beam or Brachytherapy boost can be given at the discretion of the radiation oncologist. If deemed necessary, the boost volume would include the positive tumor margin (residual tumor) plus a margin of 1 cm. Boost treatment should be delivered within 2 weeks following surgery or after adequate wound healing has occurred.

The target volume for postoperative radiotherapy will be the residual tumor bed as defined by the surgical and pathological findings.

### 5.7.10 **External Beam Radiotherapy**

Postoperative external beam boost dose is 16 Gy in 8 fractions (once a day) for microscopic disease and 20 Gy in 10 fractions for gross residual disease providing normal tissue is spared (likely requires a biologic or synthetic tissue spacer).

### 5.7.11 **Anticipated Radiation Therapy Adverse Events**

Acute: Wound complications of any grade are expected to develop in about one third of patients. Other common radiation adverse events include: fatigue, regional alopecia, diarrhea, skin erythema and desquamation within the treatment fields, and reduction in blood counts.

Long-term: Common long-term treatment adverse events include: lymphedema of the extremity receiving radiation and surgery, subcutaneous fibrosis, and joint stiffness. Much less common radiation adverse events include bowel injury, osteoradionecrosis, and bony fracture in the radiation field. There also is a risk of secondary malignancy occurring in the irradiated field.

## **5.8 General Concomitant Medication and Supportive Care Guidelines**

Patients should receive full supportive care, including transfusions of blood and blood products, antibiotics, etc., when appropriate. The reason(s) for treatment, dosage, and the dates of treatment should be recorded.

Throughout the study, investigators may prescribe any concomitant medications or treatments deemed necessary to provide adequate supportive care. All prescription and nonprescription concomitant medication administered up to 28 days prior to enrollment, on an ongoing basis at enrollment, as well as changes in such concomitant medication, and any new concomitant medication taken while the subject is on study, should be recorded up to 30 days after the last dose of ascorbate.

**5.8.1 Antiemetics.** Use Zofran (ondansetron) with caution as this medication may be less effective when used with ascorbate. Prefer alternative agents such as prochlorperazine

**5.8.2 Fluid intake.** Subjects will be encouraged to maintain adequate hydration to decrease the risk of nephrolithiasis. Those unable to maintain oral hydration should be considered for

supplemental IV hydration per institutional care guidelines.

5.8.3 **For diabetics**, be aware high-dose ascorbate can provide false results for finger-stick glucose readings. This effect is dose dependent but can last up to 6h post-infusion. Serum/plasma tests are not affected.

## 5.9 Criteria for removal from study

Treatment with pharmacological ascorbate may be discontinued if any one of the following criteria is met:

- Intercurrent illness that prevents further administration of treatment,
- Unacceptable adverse event(s),
- Patient decides to withdraw from the study, or
- General or specific changes in the patient's condition render the patient unacceptable for further treatment in the judgment of the investigator
- Progressive disease as determined by the investigator
- A female subject becomes pregnant or fails to use 2 highly effective methods of contraception (for those subjects who are able to conceive).
- A female subject breast feeds while on study treatment.
- A male subject fails to use a highly effective method of contraception

## 5.10 Duration of Follow Up

Post-operatively subjects should be followed either by clinic visit or phone contact every  $12 \pm 4$  weeks for approximately 2 years from the end of enrollment, to assess for survival, and disease recurrence. Surveillance imaging and clinical assessment to assess for disease recurrence will be as per NCCN guidelines.

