## Ascorbate Dose Levels

[figure not shown]
Dose 0      Ascorbate 75 gm IV three times weekly concurrently with radiation  
Dose -1      Ascorbate 62.5 gm IV three times weekly concurrently with radiation  
•      Initial dose for all = Ascorbate 75gm IV

## 5.3 Phase 2

[figure not shown]
The phase 2 part of the study will provide an estimate of the relative treatment effect of pharmacological ascorbate in combination with preoperative EBRT in subjects with locally advanced, resectable, extremity or retroperitoneal high grade sarcomas, as measured by pathological response rates.

As above, patients will receive the first dose of pharmacological ascorbate intravenously on day 1 of week 1 provided no reactions are seen to the test dose. This will be followed by 3 times a week dosing (= 15 doses total) at Dose 0 until completion of EBRT. Standard doses of radiation for resectable soft tissue sarcomas according to the NCCN sarcoma guidelines will be administered. Patients will receive preoperative radiation at a dose of 50 Gy over 25 fractions for extremity and trunk sarcoma or 45 to 50.4 Gy in 28 fractions for retroperitoneal sarcomas starting on week 1 day 1. Subjects should be followed either by clinic visit or phone contact every 12 weeks (+/- 4 weeks) for approximately 24 months after the end of the treatment phase, at which time the initial survival data and disease recurrence will be assessed. Details as per study calendar (Section 10).

[figure not shown]

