## 10. STUDY CALENDAR

### 10.1 Study Procedures

	Screen b	Treatment a					Off treatment and end of study c	Follow Up d
		Week 1	Week 2	Week 3	Week 4	Week 5 (+1wk j )		
H & P	X	X		X		X		
Tumor biopsy (optional)	X b							
Performance status	X						X	X
Clinical MRI/ Staging CT	X						X	X e
Pregnancy test k (urine)	X							
G6PD	X							
EKG	X							
CBC w/diff	X			X		X		
PT/INR, PTT & uric acid	X							
Height	X							
Weight, BSA	X						X	
Vitals (BP, pulse) m	X	X	x	X	x	X	X	
Comprehensive metabolic panel (CMP)	X	X		X		X	X	
Ascorbate infusion	X i	XXX	XXX	XXX	XXX	XXX		
Blood for ascorbate levels f	X	X		X		X		
ROS Research blood g	X	X		X		X	X	
Immunology research lab g	X					X	X	
Iron Panel including ferritin h	X						X	
T2* /QSM and DWI MR imaging sequences (optional)	X			X			X	
Adverse Events & Con Meds			X	X	X	X	X	

**a** study day 1 is defined as radiation therapy day 1 (i.e., fraction 1).

**b** screening labs, history, and physical must be obtained  $\leq$  28d from d1. G6PD may be obtained at any time prior to test dose. MRI/CT obtained  $\leq$  28d from d1 (RT sim is acceptable). Pregnancy test per institutional guidelines. Optional tumor biopsy can be done anytime before week 1 dosing.

**c** includes both off-treatment evaluation and study completion. Study completion requires a final study dictated visit 4 to 6 weeks after the last dose of ascorbate. Follow at least monthly until resolution of all ascorbate related adverse events.

**d** approx every 3 months (every 12 weeks [+/- 4 weeks]) for overall survival through passive chart review, phone call or scheduled follow-up visit for 2 years

**e** Imaging as per standard of care for site specific sarcomas

**f** 4cc green-top Na-Heparin tube. Draw pre-infusion at 15g dose, then 30 min post-infusion: week 1 day 1 , week 3 and last infusion of week 5

**g** 6cc pink-top EDTA tube. Draw pre infusion The specimen should be placed on ice immediately after draw and carried to the lab

**h** At time of screening and end of study

**i** Test dose of 15 g intravenously once G6PD levels confirmed to be adequate. A physician must review the patient's medication list against the list of medications prohibited on this trial prior to the test dose of ascorbate.

**j** In case of radiation treatment delays due to holidays

**k**  $\pm 7$  days prior to day 1

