## **10.3 Post-treatment Evaluations**

Following surgical resection of primary tumor, patients will be followed as per NCCN guidelines for approximately 2 years for survival data and disease recurrence.

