**Response Measurement Criteria:**

Measurements of the tumor in its largest dimension should be obtained at baseline and at the end of the treatment phase, prior to surgical resection.

Response criteria should be by RECIST v 1.1.

- Complete response is the disappearance of all target lesions.
- Partial response is a 30% decrease in the sum of the longest dimensions of the target lesions, relative to baseline.
- Progressive disease is an increase of 20% or more in the sum of the longest dimension of target lesions
- Stable disease is a decrease in the tumor size of < 30% or an increase of < 20%.
- Antitumor response by pathologic assessment will be performed on the resected tumors. Pathologic assessment will be performed per institutional guidelines.
- The percent of tumor necrosis and the percent of tumor-infiltrating lymphocytes will be documented.
- Complete pathological response will be considered  $\geq 95\%$  pathologic tumor necrosis.

Radiologic response will be evaluated in this study using the new international criteria proposed by the revised Response Evaluation Criteria in Solid Tumors (RECIST) guideline (version 1.1) [*Eur J Ca* 45:228-247, 2009]. Changes in the largest diameter (unidimensional measurement) of the tumor lesions and the shortest diameter in the case of malignant lymph nodes are used in the RECIST criteria.

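### Sections 5.3, 5.10, 10.3 and calendar footnote d give conflicting follow-up rules, and a treated subject who is not resected may have no planned recurrence contacts

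*Combined protocol and SAP*

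**What the plan says.** Section 5.10 opens: "Post-operatively subjects should be followed either by clinic visit or phone contact every" 12 weeks, give or take 4. It continues "for approximately 2 years from the end of enrollment, to assess for survival, and disease recurrence". It does not say whether the end of enrollment means the close of trial accrual or the subject's own enrollment.

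Section 10.3 reads: "Following surgical resection of primary tumor, patients will be followed as per NCCN guidelines for approximately 2 years for survival data and disease recurrence".

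Section 5.3, under the Phase 2 heading, has contacts at the same interval "for approximately 24 months after the end of the treatment phase, at which time the initial survival data and disease recurrence will be assessed". Section 11.3 places the pre-operative tumor measurement "at the end of the treatment phase, prior to surgical resection", so the treatment phase is over before surgery and the starting point in 5.3 is not the one in 5.10 and 10.3. Section 5.2, the Phase 1b counterpart, has no long-term follow-up sentence.

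In the Section 10.1 calendar, footnote d provides roughly three-monthly follow-up "for overall survival through passive chart review, phone call or scheduled follow-up visit for 2 years". It gives no starting date and does not mention recurrence. Footnote e, on follow-up scans, says "Imaging as per standard of care for site specific sarcomas".

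The endpoint table in Section 3 counts both TTP and survival from the first treatment day and estimates survival at 2 years. Section 11.2 starts TTP at enrollment. Section 12.2 names Kaplan-Meier for both endpoints and gives no censoring rule or cutoff date.

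**The concern.** Staff cannot tell from these sections whom to contact, for what, from when, or until when. The gap that matters is the subject who starts ascorbate and radiation but is never resected. Sections 5.10 and 10.3 tie recurrence follow-up to surgery, so on their wording that subject is not covered.

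The route is plausible. Section 5.9 allows ascorbate to stop for illness, adverse events, investigator judgment or progression. Section 6.3 can take a subject off study after a repeat DLT or a long delay. Neither says what follow-up comes next. Section 4.1.6 admits stage IV disease, where planned surgery may not take place.

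Subjects who stop before resection are plausibly at higher risk than those who reach it. If they leave recurrence follow-up for that reason, censoring is informative and the TTP curve is likely to look too favorable.

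**Working it through.** **1. The plan's own figure.** The only computed design figure is the primary test in Section 12.2: n = 25, success at 6 or more responders, 10% against 30%. By the exact binomial, P(X ≥ 6 | 25, 0.10) = 0.0334 and P(X ≥ 6 | 25, 0.30) = 0.8065. These match the stated 0.03 and 81%. The calculation uses no follow-up data, so this point does not touch it.

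**2. The four rules side by side.**

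| Place | Applies to | Starts | Ends | Purpose |
|---|---|---|---|---|
| 5.3 | Phase 2 text | end of treatment phase | about 24 months later | survival and recurrence |
| 5.10 | no phase named | after surgery | about 2 years from end of enrollment (two readings) | survival and recurrence |
| 10.3 | no phase named | after resection | about 2 years | survival and recurrence |
| Footnote d | no phase named | not stated | 2 years | survival |

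**3. Where follow-up ends, in months from the first treatment day.**

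Inputs:
- Radiation takes 35 days (25 fractions) or 39.2 days (28 fractions at five a week, assumed). Source: Section 5.7.
- Surgery follows 4 to 6 weeks after radiation, i.e. 28 to 42 days. Source: Section 5.1.
- Accrual is 2 a month to 25 patients. Source: Section 12.3.
- Enrollment to day 1 is 0 to 28 days. This is an assumption; 28 days is the screening window in Section 10.2.
- One month is 30.4375 days.

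Results:
- Surgery falls between day 35 + 28 = 63 and day 39.2 + 42 = 81.2, about weeks 9 to 11.6. The start in 5.3 is therefore 4 to 6 weeks earlier than in 5.10 and 10.3.
- 5.3: 24 + 35/30.4375 = 25.1, to 24 + 39.2/30.4375 = 25.3.
- 10.3, counting 2 years from surgery: 24 + 63/30.4375 = 26.1, to 24 + 81.2/30.4375 = 26.7.
- 5.10 read as close of accrual: accrual takes 25/2 = 12.5 months, so the end is 24 + 12.5 = 36.5 for the first subject and about 24 for the last. If six are treated at Dose 0 and then 25 at Dose -1, accrual is 31/2 = 15.5 months and the first subject's end is 39.5.
- 5.10 read as the subject's own enrollment: 24 − 28/30.4375 = 23.1, to 24.0.

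**4. Tracing an unresected subject.**
- In Phase 2, 5.3 applies and plans contacts for recurrence and survival whether or not surgery takes place.
- In Phase 1b, 5.3 does not apply on its face, and 5.10 and 10.3 start only after surgery. What remains is footnote d (survival contacts), the off-treatment scan in the calendar, and footnote e (standard-of-care imaging with no fixed schedule or end date). No passage plans recurrence contacts.
- Section 12.3 includes Phase 1b subjects treated at the RP2D in the Phase II portion. Declaring that dose takes six subjects, so 6/25 = 24% of the analysis set comes from the phase with the gap.

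**5. Effect on each endpoint.** Unequal administrative follow-up does not by itself bias Kaplan-Meier. Bias needs subjects to leave for reasons linked to outcome. That can happen for TTP under 5.10 and 10.3. It is less likely for survival, since footnote d does not depend on surgery. The documents give no expected number of unresected subjects, so no size of bias can be calculated.

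**The case against.** The strongest reply is that the calendar already covers these subjects. Its follow-up column has imaging and performance status as well as survival contacts, none of it conditional on surgery, and there is an off-treatment scan. Section 5.3 covers Phase 2, and Section 12.3 might be read as bringing the Phase 1b subjects under it. Section 5.9 governs stopping ascorbate, which does not cancel surgery. A subject stopped for progression already has the TTP event. The endpoints are secondary and descriptive.

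Most of this stands and narrows the point. The TTP exposure is confined to unresected subjects who have not already progressed, chiefly in Phase 1b. But 12.3 says who is counted in Phase II; it does not give those subjects the 5.3 schedule. Standard-of-care imaging with no stated timing is also not a planned recurrence assessment. The four rules remain unreconciled.

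A reader might go further and infer one of the following:
- **Unresected subjects will have no progression follow-up.** The documents support only that they may have none.
- **Two-year survival is inflated because only post-operative subjects are followed.** Footnote d contradicts this, and a subject lost early would be censored, not removed from the analysis.
- **The 2-year survival point lies beyond most censoring times.** This needs the per-subject reading of 5.10. Even then the shortfall is at most about 28 days, under an assumed screening interval and a duration given as approximate.
- **Passive chart review misses deaths.** The documents offer no evidence on this, and footnote d also lists calls and visits.

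**Conclusion.** The conflict is real. Start points differ by 4 to 6 weeks. Planned ends run from about 23.1 to 36.5 months after first treatment at the stated accrual, or 39.5 if 31 subjects are treated. These ranges rest on five fractions a week and 0 to 28 days from enrollment to day 1.

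The consequence is a risk of informative censoring of TTP for treated, unresected subjects, most clearly in Phase 1b. It is compounded by two time origins for TTP and the lack of a censoring rule. Its size cannot be stated from the documents. Survival is less exposed, and the primary pCR test is unaffected. This should be corrected, but it does not threaten the trial's main conclusion.

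**What to change.** State one rule in 5.3, 5.10, 10.3 and footnote d, for both phases:

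- **Who:** every subject who starts study treatment on or after day 1, resected or not, unless consent for follow-up is withdrawn. Test-dose screen failures (Section 5.5) are excluded.
- **What and how often:** contact every 12 (+/- 4) weeks for both recurrence and survival.
- **Until when:** a final contact at or after 24 months from the first day of study treatment. Replace the end-of-enrollment anchor in 5.10 with this one, and remove surgery as a condition for follow-up in 5.10 and 10.3.
- **TTP origin:** change 11.2 to the first day of study treatment, as in Section 3.
- **Censoring, in 12.2:** TTP at the last disease assessment, survival at the last date known alive.

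Imaging stays standard of care, and chart review can remain as footnote d allows. The cost is amendment wording and a few extra phone contacts, with no new procedures.

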# 6. DOSING DELAYS/DOSE MODIFICATIONS/ DOSE LIMITING TOXICITIES

## 6.1 Radiation Therapy

- 6.1.1 **Dose modification** - Radiation therapy dose will not be modified.
- 6.1.2 **Treatment delay** - Will only occur for reasons of safety due to intercurrent illness or medical conditions that in the judgment of the radiation oncologist forbid delivery of radiation therapy.
- 6.1.3 **Interruptions** or delays of greater than three days should be discussed with the study's principal investigator and documented

## 6.2 Ascorbate Therapy

- 6.2.1 **Dose reductions** – As per Table 1 (below) if there is a DLT (Section 5.6)

**Table 1. Phase 1b Dose De-escalation Schedule**

Number of Patients with DLT at a Given Ascorbate Dose	Decision Rule
$\geq 2$	Dose level will be declared toxic. If this is the lowest dose level, stop the study due to excessive toxicity; otherwise enter three additional patients at the next lowest dose level.
$\leq 1$ out of 3	Enter three more patients at this dose level.
$\leq 1$ out of 6	This is the recommended dose for the subsequent Phase2.

## Ascorbate Dose Levels

Dose 0	Ascorbate 75 gm IV three times weekly concurrently with radiation
Dose -1	Ascorbate 62.5 gm IV three times weekly concurrently with radiation
	• Initial dose for all = Ascorbate 75gm IV

6.2.2 **Test/retest.** If an unexpected adverse event is observed, the treating physicians may withhold ascorbic acid for up to 2 calendar weeks to determine if the effect diminishes or resolves entirely. Considering the nature and severity of the event, if reasonable ascorbic acid should then be continued to determine if the event again presents. This will function as a test for causality.

6.2.3 **Dose delays.** Due to holidays or inclement weather, doses may be delayed by up to one week with physician and PI approval. Reason for treatment delay should be noted in the study chart.

## 6.3 Dose Limiting Toxicities

### Definitions of dose-limiting toxicity:

Toxicity will be evaluated according to CTCAE version 5.0. DLT will be defined as any of the following ascorbate related toxicity or related to the combination of pharmacologic ascorbate and radiation therapy during treatment and up to 28 days after the first pharmacologic ascorbate infusion:

- Infection grade 4
- SAE per 21CFR312.21 with an attribution of *possible, probable, or definite* to ascorbate
- Grade 3 diarrhea or nausea/vomiting despite maximal support
- Any grade 3/4 or greater hematologic or non-hematologic toxicity not explainable by another cause in the opinion of the principal investigator, with the exceptions of:
  - Expected radiation related skin toxicity of any grade.
  - Brief (< 1 week) grade 3 fatigue.

If unexpected DLT occurs, ascorbate administration should be delayed until the DLT has resolved to at least CTCAE version 5.0 grade 1 or baseline and future dose be reduced to dose level -1 as per table 1. If dosing is delayed by more than 4 weeks due to the occurrence of unexpected adverse event or if a patient already dose reduced to level -1 (62.5 gm/dose) experiences another DLT that is considered related to ascorbate, then the subject should be taken off study.

